3.2.5 Clinical Monitoring for the CIV rhIL-15 infusion

The rhIL-15 is given by continuous infusion, and the safety of combined administration will be confirmed by administering Cycle 1 treatment as an inpatient and the patient may continue treatment as an outpatient if they satisfy the criteria listed above in Section 3.2. It is likely that the majority of patients will receive their CIV rhIL-15 as inpatients and will have regular VS assessment as per nursing unit norms. Patients who experience a decrease in their BP below 100 mmHg or have symptomatic orthostatic changes in the BP will receive NS infusion to increase their BP and alleviate their symptoms. These patients may also receive salt poor albumin (25%) and or transfused packed red blood cells (RBCs) as clinically indicated by their monitoring laboratories. Patients who experience shortness of breath or have decrease in their oxygen saturations below 92% will receive Lasix IV, intermittent low flow oxygen (grade 2 CTC event) and respiratory treatments as clinically indicated to improve their blood oxygen levels. Patients who experience these events will have more frequent VS and clinical assessments as per institutional norms. After Cycle 1 monitoring for dose limiting toxicities, patients may also have brief interruptions (< 2 hours) of their CIV rhIL-15 to allow symptoms to decrease to acceptable levels.

3.2.5.1 Vital Signs during Inpatient treatment

Inpatient: patients will have vital signs (BP, HR, RR, temperature and oxygen saturation) obtained as per inpatient unit norms.

3.2.5.2 Vital Signs for Outpatient treatment

Outpatient: patients will have vital signs (BP, HR, RR, temperature and oxygen saturation) obtained at the time of their visit to have their infusion bag changed.

3.3 DOSE MODIFICATIONS

3.3.1 rhIL-15-specific Adverse Events

Please refer to the Comprehensive Adverse Event and Potential Risk list (CAEPR) for rhIL-15 presented in Section [14.1.8](#).

For patients treated later in the phase II dose expansion cohort (Cohort 2) at 4 mcg/kg, CIVrhIL-15 infusion may be interrupted and the dose reduced to 3 mcg/kg for patients who have reversible grade 3 thrombocytopenia, hypoxia, symptomatic hypotension or 3 LFT abnormalities during the CIV rhIL-15 infusion for improved general tolerability. After the safety of the 4 mcg/kg dose level has been established, patients treated in the phase II dose expansion cohort who poorly tolerate the 4 or 3 mcg/kg dose level (significant fatigue or anorexia) will also have the option of further dose reduction to the 2 mcg/kg dose level. Patients who are unable to tolerate the reduced dose of rhIL-15 will discontinue cytokine treatment and may continue treatment with Avelumab.

Dose of rhIL-15 is based on the dose level and patient's weight at the beginning of each cycle and can only be modified for rounding and/or consistency with prior cycles or as specified above, and not for adverse events or renal/hepatic dysfunction. Infusion may continue during correction of electrolyte and other laboratory abnormalities listed in Section [3.1.1](#). Infusion may be interrupted for up to two hours each day, but treatment should end 120 (± 1) hours after initiation on Day 1.

3.3.2 Avelumab

3.3.2.1 Treatment modifications for symptoms of infusion-related reactions

Table 8: Treatment modifications for infusion-related reactions

NCI-CTCAE Grade	Treatment Modification for Avelumab
Grade 1 – mild Mild transient reaction; infusion interruption not indicated; intervention not indicated.	Decrease the avelumab infusion rate by 50% and monitor closely for any worsening.
Grade 2 – moderate Therapy or infusion interruption indicated but responds promptly to symptomatic treatment (for example, antihistamines, NSAIDs, narcotics, IV fluids); prophylactic medications indicated for ≤ 24 h.	Temporarily discontinue avelumab infusion. Resume infusion at 50% of previous rate once infusion-related reaction has resolved or decreased to at least Grade 1 in severity, and monitor closely for any worsening.
Grade 3 or Grade 4 – severe or life-threatening Grade 3: Prolonged (for example, not rapidly responsive to symptomatic medication and/or brief interruption of infusion); recurrence of symptoms following initial improvement; hospitalization indicated for clinical sequelae. Grade 4: Life-threatening consequences; urgent intervention indicated.	Stop avelumab infusion immediately and disconnect infusion tubing from the subject. Subjects have to be withdrawn immediately from study avelumab and must not receive any further avelumab treatment.
If avelumab infusion rate has been decreased by 50% or interrupted due to an infusion reaction, it must remain decreased for the next scheduled infusion. If no infusion reaction is observed in the next scheduled infusion, the infusion rate may be returned to baseline at the subsequent infusions based on investigator's medical judgment. If hypersensitivity reaction occurs, the subject must be treated according to the best available medical practice.	

IV = intravenous; NCI-CTCAE = National Cancer Institute-Common Terminology Criteria for Adverse Event; NSAIDs = nonsteroidal anti-inflammatory drugs

3.3.2.2 Treatment modifications for immune-related adverse reactions (irAE)

All grading scales in the following tables are according to the revised NCI Common Terminology Criteria for Adverse Events (CTCAE) version 5.0.

Table 9: Treatment Modification for Gastrointestinal Immune-related AEs

Gastrointestinal irAEs		
Severity of Diarrhea/Colitis	Initial Management	Follow-up Management
Grade 1 Diarrhea: increase < 4 stools/day over Baseline; mild increase in ostomy output compared to baseline Colitis: asymptomatic	Continue avelumab therapy Symptomatic treatment (e.g., loperamide)	Close monitoring for worsening symptoms Educate subject to report worsening immediately If worsens: Treat as Grade 2, 3 or 4.

Gastrointestinal irAEs		
Severity of Diarrhea/Colitis	Initial Management	Follow-up Management
Grade 2 Diarrhea: 4 to 6 stools per day over Baseline; moderate increase in ostomy output compared to baseline; limiting instrumental ADL IV fluids indicated < 24 hours; not interfering with ADL Colitis: abdominal pain; mucus or blood in stool	Withhold avelumab therapy Symptomatic treatment	If improves to Grade \leq 1: Resume avelumab therapy If persists $>$ 5-7 days or recurs: Treat as Grade 3 or 4.
Grade 3 to 4 Diarrhea (Grade 3): increase of \geq 7 stools per day over Baseline; hospitalization indicated; severe increase in ostomy output compared to baseline; limiting self-care ADL incontinence; IV fluids \geq 24 h; interfering with ADL Grade 4: Life-threatening consequences; urgent intervention indicated Colitis (Grade 3): severe abdominal pain, medical intervention indicated, peritoneal signs Grade 4: life-threatening, urgent intervention indicated perforation	Withhold avelumab for Grade 3. Permanently discontinue avelumab for Grade 4 or recurrent Grade 3. 1 to 2 mg/kg/day prednisone IV or equivalent Add prophylactic antibiotics for opportunistic infections Consider lower endoscopy	If improves: Continue steroids until Grade \leq 1, then taper over at least 1 month; resume avelumab therapy following steroids taper (for initial Grade 3). If worsens, persists $>$ 3 to 5 days, or recurs after improvement: Add infliximab 5mg/kg (if no contraindication). Note: infliximab should not be used in cases of perforation or sepsis.

Table 10: Treatment Modifications for Dermatological Immune-related AEs

Dermatological irAEs		
Rash	Initial Management	Follow-up Management
Grade 1 to 2 Covering \leq 30% body surface area	Continue avelumab Symptomatic therapy (for example, antihistamines, topical steroids)	If persists $>$ 1 to 2 weeks or recurs: Consider skin biopsy Withhold avelumab Consider skin biopsy Consider 0.5 to 1 mg/kg/day prednisone or equivalent. Once improving, taper steroids over at least 1 month, consider prophylactic antibiotics for opportunistic infections, and resume avelumab following steroids taper. If worsens: Treat as Grade 3 to 4

Dermatological irAEs		
Rash	Initial Management	Follow-up Management
Grade 3 to 4 Covering > 30% body surface area; life threatening consequences	Withhold avelumab for Grade 3 Permanently discontinue for Grade 4 or recurrent Grade 3 Consider skin biopsy Dermatology consult 1 to 2 mg/kg/day prednisone or equivalent Add prophylactic antibiotics for opportunistic infections	If improves to Grade ≤ 1 : Taper steroids over at least 1 month and add prophylactic antibiotics for opportunistic infections

Table 11: Treatment Modifications for Pulmonary Immune-related AEs

Pulmonary irAEs		
Pneumonitis	Initial Management	Follow-up Management
Grade 1 Radiographic changes only	Consider withholding avelumab Monitor for symptoms every 2 to 3 days Consider Pulmonary and Infectious Disease consults	Re-assess at least every 3 weeks If worsens: Treat as Grade 2 or Grade 3 to 4
Grade 2 Mild to moderate new symptoms	Withhold avelumab Pulmonary and Infectious Disease consults Monitor symptoms daily, consider hospitalization 1 mg/kg/day prednisone or equivalent Add prophylactic antibiotics for opportunistic infections Consider bronchoscopy, lung biopsy	Re-assess every 1 to 3 days If improves: When symptoms return to Grade ≤ 1 , taper steroids over at least 1 month and then resume avelumab following steroids taper If not improving after 2 weeks or worsening: Treat as Grade 3 to 4
Grade 3 or 4 Grade 3: Severe new symptoms; New / worsening hypoxia; Grade 4: Life-threatening	Permanently discontinue avelumab Hospitalize Pulmonary and Infectious Disease consults 1 to 2 mg/kg/day prednisone or equivalent Add prophylactic antibiotics for opportunistic infections Consider bronchoscopy, lung biopsy	If improves to Grade ≤ 1 : Taper steroids over at least 1 month If not improving after 48 hours or worsening: Add additional immunosuppression (for example, infliximab, cyclophosphamide, IV immunoglobulin, or mycophenolate mofetil)

Table 12: Treatment Modifications for Hepatic Immune-related AEs

Hepatic irAEs		
Liver test elevation	Initial Management	Follow-up Management
Grade 1 Grade 1 AST or ALT > ULN to 3.0 x ULN and / or total bilirubin > ULN to 1.5 x ULN	Continue avelumab	Continue liver function monitoring If worsens: Treat as Grade 2 or 3 to 4
Grade 2 AST or ALT > 3.0 to \leq 5 x ULN and/or total bilirubin > 1.5 to \leq 3 x ULN	Withhold avelumab Increase frequency of monitoring to every 3 days	If returns to Grade \leq 1: Resume routine monitoring, resume avelumab If elevations persist > 5 to 7 days or worsen: Treat as Grade 3 or 4
Grade 3 to 4 AST or ALT > 5 x ULN and/or total bilirubin > 3 x ULN	Permanently discontinue avelumab Increase frequency of monitoring to every 1 to 2 days 1 to 2 mg/kg/day prednisone or equivalent Add prophylactic antibiotics for opportunistic infections Consult gastroenterologist/ hepatologist Consider obtaining MRI/CT scan of liver and liver biopsy if clinically warranted	If returns to Grade \leq 1: Taper steroids over at least 1 month and add prophylactic antibiotics for opportunistic infections If does not improve in > 3 to 5 days, worsens or rebounds: Add mycophenolate mofetil 1 gram (g) twice daily If no response within an additional 3 to 5 days, consider other immunosuppressants per local guidelines

Table 13: Treatment Modifications for Renal Immune-related AEs

Renal irAEs		
Creatinine Increase	Initial Management	Follow-up Management
Grade 1 Creatinine increased > ULN to 1.5 x ULN	Continue avelumab	Continue renal function monitoring If worsens: Treat as Grade 2 or 3 to 4
Grade 2 to 3 Creatinine increased > 1.5 and \leq 6 x ULN	Withhold avelumab Increase frequency of monitoring to every 3 days 1 to 2 mg/kg/day prednisone or equivalent. Add prophylactic antibiotics for opportunistic infections Consider renal biopsy	If returns to Grade \leq 1: Taper steroids over at least 1 month, and resume avelumab following steroids taper. If worsens: Treat as Grade 4.

Renal irAEs		
Creatinine Increase	Initial Management	Follow-up Management
Grade 4 Creatinine increased > 6 x ULN	Permanently discontinue avelumab Monitor creatinine daily 1 to 2 mg/kg/day prednisone or equivalent. Add prophylactic antibiotics for opportunistic infections Consider renal biopsy Nephrology consult	If improves to Grade \leq 1: Taper steroids over at least 1 month

Table 14: Treatment Modifications for Cardiac Immune-related AEs

Cardiac irAEs		
Myocarditis	Initial Management	Follow-up Management
New onset of cardiac signs or symptoms and / or new laboratory cardiac biomarker elevations (e.g., troponin, CK-MB, BNP) or cardiac imaging abnormalities suggestive of myocarditis	Withhold avelumab. Hospitalize. In the presence of life threatening cardiac decompensation, consider transfer to a facility experienced in advanced heart failure and arrhythmia management. Cardiology consult to establish etiology and rule out immune- mediated myocarditis. Guideline based supportive treatment as per cardiology consult.* Consider myocardial biopsy if recommended per cardiology consult.	If symptoms improve and immune-mediated etiology is ruled out, re-start avelumab. If symptoms do not improve/worsen, viral myocarditis is excluded, and immune-mediated etiology is suspected or confirmed following cardiology consult, manage as immune-mediated myocarditis.
Immune-mediated myocarditis	Permanently discontinue avelumab. Guideline based supportive treatment as appropriate as per cardiology consult.* 1 to 2 mg/kg/day. prednisone or equivalent Add prophylactic antibiotics for opportunistic infections.	Once improving, taper steroids over at least 1 month. If no improvement or worsening, consider additional immunosuppressants (e.g., azathioprine, cyclosporine A)

*Local guidelines, or e.g., European Society of Cardiology or American Heart Association guidelines

European Society of Cardiology guidelines website: <https://www.escardio.org/Guidelines/Clinical-Practice-Guidelines>

American Heart Association guidelines website:
<http://professional.heart.org/professional/GuidelinesStatements/searchresults.jsp?q=&y=&t=1001>

Table 15: Treatment Modifications for Endocrine Immune-related AEs

Endocrine irAEs		
Endocrine disorder	Initial Management	Follow-up Management
Grade 1 or Grade 2 endocrinopathies (hypothyroidism, hyperthyroidism, adrenal insufficiency, type I diabetes mellitus)	Continue avelumab Endocrinology consult if needed Start thyroid hormone replacement therapy (for hypothyroidism), anti-thyroid treatment (for hyperthyroidism), corticosteroids (for adrenal insufficiency) or insulin (for Type I diabetes mellitus) as appropriate. Rule-out secondary endocrinopathies (i.e., hypopituitarism / hypophysitis)	Continue hormone replacement/suppression and monitoring of endocrine function as appropriate.
Grade 3 or Grade 4 endocrinopathies (hypothyroidism, hyperthyroidism, adrenal insufficiency, type I diabetes mellitus)	Withhold avelumab Consider hospitalization Endocrinology consult Start thyroid hormone replacement therapy (for hypothyroidism), anti-thyroid treatment (for hyperthyroidism), corticosteroids (for adrenal insufficiency) or insulin (for type I diabetes mellitus) as appropriate. Rule-out secondary endocrinopathies (i.e., hypopituitarism / hypophysitis)	Resume avelumab once symptoms and/or laboratory tests improve to Grade ≤ 1 (with or without hormone replacement/suppression). Continue hormone replacement/suppression and monitoring of endocrine function as appropriate.
Hypopituitarism/Hypophysitis (secondary endocrinopathies)	If secondary thyroid and/or adrenal insufficiency is confirmed (i.e., subnormal serum FT4 with inappropriately low TSH and/or low serum cortisol with inappropriately low ACTH) : 
• Refer to endocrinologist for dynamic testing as indicated and measurement of other hormones (FSH, LH, GH/IGF-1, PRL, testosterone in men, estrogens in women)• Hormone replacement/suppressive therapy as appropriate• Perform pituitary MRI and visual field examination as indicated If hypophysitis confirmed: 
• Continue avelumab if mild symptoms with normal MRI. Repeat the MRI in 1 month• Withhold avelumab if moderate, severe or life-threatening symptoms of hypophysitis and/or abnormal MRI. Consider hospitalization. Initiate corticosteroids (1 to 2 mg/kg/day prednisone or equivalent) followed by corticosteroids taper during at least 1 month.• Add prophylactic antibiotics for opportunistic infections.	Resume avelumab once symptoms and hormone tests improve to Grade ≤ 1 (with or without hormone replacement). In addition, for hypophysitis with abnormal MRI, resume avelumab only once shrinkage of the pituitary gland on MRI/CT scan is documented. Continue hormone replacement/suppression therapy as appropriate.

Table 16: Treatment Modifications for Other Immune-related AEs

Other irAEs (not described above)		
Grade of other irAEs (NCI CTCAE v5)	Initial Management	Follow-up Management
Grade 2 or Grade 3 clinical signs or symptoms suggestive of a potential irAE	Withhold avelumab pending clinical investigation	If irAE is ruled out, manage as appropriate according to the diagnosis and consider restarting avelumab If irAE is confirmed, treat as Grade 2 or 3 irAE.
Grade 2 irAE Or first occurrence of Grade 3 irAE	Withhold avelumab 1 to 2 mg/kg/day prednisone or equivalent. Add prophylactic antibiotics for opportunistic infections Specialty consult as appropriate	If returns to Grade ≤ 1 : Taper steroids over at least 1 month, and resume avelumab following steroids taper.
Recurrence of same Grade 3 irAEs	Permanently discontinue avelumab 1 to 2 mg/kg/day prednisone or equivalent. Add prophylactic antibiotics for opportunistic infections Specialty consult as appropriate	If returns to Grade ≤ 1 : Taper steroids over at least 1 month
Grade 4	Permanently discontinue avelumab 1 to 2 mg/kg/day prednisone or equivalent and/or other immunosuppressant as needed. Add prophylactic antibiotics for opportunistic infections Specialty consult	If improves to Grade ≤ 1 : Taper steroids over at least 1 month
Requirement for 10 mg per day or greater prednisone or equivalent for more than 12 weeks for reasons other than hormonal replacement for adrenal insufficiency	Permanently discontinue avelumab Specialty consult	
Persistent Grade 2 or 3 irAE lasting 12 weeks or longer		

Abbreviations: ACTH=adrenocorticotrophic hormone; ADL=activities of daily living; ALT=alanine aminotransferase; AST=aspartate aminotransferase; BNP=B-type natriuretic peptide; CK-MB=creatinine kinase MB; CT= computed tomography; FSH=follicle-stimulating hormone; GH=growth hormone; IGF-1=insulin-like growth factor 1; irAE=immune related adverse event; IV=intravenous; LH=luteinizing hormone; MRI=magnetic resonance

imaging; NCI CTCAE=National Cancer Institute Common Terminology Criteria for Adverse Events; PRL=prolactin; T4=thyroxine; TSH=thyroid stimulating hormone; ULN=upper limit of normal.

3.3.3 Unacceptable Toxicity

Occurrence of any of the adverse events listed in Section [3.1.1](#) after the first 28 days of treatment in the Dose Expansion cohort (Cohort 2) will lead to permanent discontinuation of protocol therapy, but will not be deemed a DLT for purposes of dose escalation. Any patient who requires corticosteroid treatment for an avelumab related irAE will have their rhIL-15 discontinued regardless of their perceived tolerance of the cytokine. Patients may continue single agent avelumab after halting rhIL-15 treatment if considered appropriate in the standard avelumab irAE decision algorithm.

3.4 STUDY INTERVENTION COMPLIANCE

Adherence to the protocol will be verified by reviewing the Medical Administration Record (MAR) section of the medical record, which will serve as source documentation.

3.5 ON STUDY EVALUATIONS

Prior to avelumab administration (Day 8 and 22), pre-dose assessments must be performed (up to 3 days prior). After Cycle 1, pre-dose assessments may be performed up to 3 days prior to a cycle except where otherwise noted. In the event that the patient's condition is deteriorating, laboratory evaluations should be repeated within 48 hours prior to initiation of the next cycle of therapy. The results from all procedures/tests must be reviewed prior to initiation of each cycle of treatment for consideration of dose modifications and delay of therapy.

Treatment with rhIL-15 and avelumab will continue for 4 cycles or until disease progression, unacceptable treatment-related toxicity or other reasons outlined in Section [3.9.1](#).

Refer to the Study Calendars (Section [APPENDIX F](#)) for a complete list of procedures to be performed at each scheduled study visit. See also Section [5](#) for all samples to be collected for correlative research. During treatment, it is expected that all laboratory and clinical assessments be conducted at the NIH (including post-treatment imaging evaluations); results from outside NIH will only be accepted at the discretion of the investigator.

3.6 POST-TREATMENT EVALUATIONS

Post treatment evaluations (i.e., End of Treatment Visit) will be performed approximately 30 days after the last dose of protocol treatment. If a subject initiates a new anti-cancer therapy within 30 days after the last dose of trial treatment, the 30-day safety follow-up visit must occur before the first dose of the new therapy, if possible. If the patient cannot return to the Clinical Center for this visit, a request will be made to have a local physician or laboratory collect a CBC with differential and send the results. If this is not possible, patients may be assessed by telephone or email for symptoms.

Unless otherwise noted, follow-up will occur at the following time point: every 60 days (\pm 7 days) for 6 months; then every 90 days (\pm 14 days) for 2 years; then every six months (\pm 28 days) for the duration of the study until the start of a new anti-neoplastic therapy, disease progression, death or end of study. Any other evaluations and tests should be performed as clinically indicated.

Upon disease progression or initiation of other anti-cancer therapy, contact will be for survival only until the subject is off study (i.e., every 3 months [\pm 4 weeks]) for the duration of the study. See Study Calendar (Section [APPENDIX F](#)) for additional information. Any adverse events

which are present at the time of discontinuation should be followed in accordance with the safety requirements.

Patients who are removed from study before completing protocol treatment will be followed until completion of the Safety Follow-up Visit or until death, whichever occurs first. Patients removed from study for unacceptable adverse event(s) will be followed until resolution or stabilization of the adverse event.

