3.6.1 Safety Follow-Up Visit

The safety follow-up visit should occur 30 days (± 7 days) after the last dose of trial treatment, or before the initiation of a new anti-cancer treatment, whichever comes first. Required testing is as noted in the Study Calendars (Section [APPENDIX F](#)). All AEs that occur prior to the Safety Follow-Up Visit should be recorded. Patients with an ongoing, treatment-related AE of Grade > 1 will be followed until the resolution of the AE to Grade 0-1, stabilization of the AE in the opinion of the investigator, or until the beginning of a new anti-neoplastic therapy, whichever occurs first. SAEs that occur within 30 days of the end of treatment or before initiation of a new anti-cancer treatment should also be followed and recorded.

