3.6.2 Extended Safety Follow-up

Given the potential risk for delayed immune-related toxicities, safety follow-up must be performed up to 90 (+14) days after the last dose of avelumab administration. This may be performed either via a clinic visit or via a telephone call/email with subsequent clinic visit requested in case any concerns are noted during the telephone call/email.

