3.6.3 Follow-Up Visits- Prior to Disease Progression

Patients who complete trial treatment or discontinue treatment without evidence of disease progression will move into the Follow-up Phase and may be assessed every 60 days (± 7 days) for 6 months; then every 90 days (± 14 days) for 2 years; then every six months (± 28 days) for the duration of the study after finishing treatment by radiologic imaging or other clinical assessments to monitor disease status. Every effort should be made to collect information regarding disease status until the start of new anti-neoplastic therapy, disease progression, death, or end of the study. If the patient cannot return to the Clinical Center for any of these visits, a request will be made to have a local physician or laboratory collect a CBC with differential and send the results. If this is not possible, patients may be assessed by telephone or email for symptoms.

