3.6.4 Follow-Up Visits – Survival/Post-Disease Progression

Once a subject experiences confirmed disease progression or starts a new anti-cancer therapy, the subject moves into the survival follow-up phase and should be contacted (e.g., phone, email, etc.; in-person visit not required) at least every 3 months for the duration of the study to collect information on new anti-cancer treatments received and to assess for survival status until death, withdrawal of consent, or the end of the study, whichever occurs first (see Study Calendar).

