3.9 CRITERIA FOR REMOVAL FROM PROTOCOL THERAPY AND OFF STUDY CRITERIA

Prior to removal from study, effort must be made to have all patients complete a safety visit approximately 30 days following the last dose of study therapy. Additional safety visits and follow-up will continue as per Section **3.6**.

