16.6 APPENDIX F: STUDY CALENDAR

Procedure	Screening	Baseline	Study Cycles						Disease Evaluations	End of Treatment and Disease Progression	Post-Treatment Follow-Up		
			C1 ¹			C2-4					Safety ²	Follow-Up (Prior to PD)	Survival (Post-PD)
Scheduling Window (Days):	-28 to -1 ³		-14 ⁴	8 (-3)	22 (-3)	1 (-3)	8 (-3)	22 (-3)	After C2 and C4 ⁵	Treatment discon/PD ⁶	Day 30 (+7)	Every 60 or 90 days ⁷	Every 3 months ⁸
Confirmation of Diagnosis ⁹	X												
Physical Exam and ECOG PS ¹⁰	X	X		X	X	X	X	X		X	X	X	
CBC with Differential	X	X	X	X	X	X	X	X		X	X	X	
Reticulocyte Count	X	X	X	X	X	X	X	X		X	X	X	
Chemistry Panels ¹¹	X	X	X	X	X	X	X	X		X	X	X	
LDH, Serum Lipase and Amylase	X	X	X	X	X	X	X	X		X	X	X	
PT/INR and aPTT	X	X	X			X				X	X	X	
Thyroid Function (i.e., TSH, T4)	X	X	X			X				X	X	X	
Urinalysis	X	X	X			X				X			
Pregnancy Test (urine/serum; WOCPB)	X	X	X										
Hepatitis B and C, HIV Antibody, HTLV-1/2	X												
Anti-nuclear antibody (ANA), rheumatoid factor (RF) and anti-thyroid antibody	X	X											
IL-2R		X	X			X							
Creatine phosphokinase (CPK), troponin	X	X	X							X		X	
Pulmonary function tests (PFTs) and TTE ¹²	X												
T, B, NK cell subsets		X		X		X	X			X	X	X	
Imaging studies ¹³	X	X							X	X		X	
MRI Lumbar Puncture ¹⁴		X							X	X		X	

Procedure	Screening	Baseline	Study Cycles						Disease Evaluations	End of Treatment and Disease Progression	Post-Treatment Follow-Up		
			C1 ¹			C2-4					Safety ²	Follow-Up (Prior to PD)	Survival (Post-PD)
Scheduling Window (Days):	-28 to -1 ³		-14 ⁴	8 (-3)	22 (-3)	1 (-3)	8 (-3)	22 (-3)	After C2 and C4 ⁵	Treatment discon/PD ⁶	Day 30 (+7)	Every 60 or 90 days ⁷	Every 3 months ⁸
Flow Cytometry ¹⁵		X		X	X		X	X	X	X	X	X	
Clinical photography ¹⁶		X							X	X		X	
Radiologic Evaluation/ tumor measurement ¹⁷		X							X	X		X	
EKG	X												
Symptoms/Adverse Events Assessment, Concomitant Medication Review	X	X				X				X	X	X	
Research Blood/Tissue Samples ¹⁸		X	Refer to Table Section 5.1										
Survival Status													X

¹ On Day 8 and Day 22 of Cycle 1, vital signs ([VS] blood pressure, pulse, respiratory rate, temperature, oxygen saturation) will be assessed predose of avelumab (within 15 minutes of injection and/or infusion), and then every 15 minutes from the start of avelumab infusion for at least 2 hours. If vital signs are not stable after 2 hours, then continue monitoring every 15 minutes until stable on 2 consecutive repeated measurements.

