² 30 days (+7) following last dose, and 90 days (+14) after last dose of avelumab (via clinic or phone/email). If initiating new anti-cancer therapy within 30 days after last dose of avelumab, 30-day safety follow-up visit must occur before first dose of new therapy.

³ Screening and Baseline evaluations should be performed within 28 days prior to enrollment and dosing, respectively, unless otherwise noted and with the following exceptions: Confirmation of diagnosis (no time limit); HIV antibody, Hepatitis B surface antigen and Hepatitis C antibody and EKG (all within 3 months) **NOTE:** Any screening tests performed within the specified time frame for baseline do not need to be repeated.

⁴ Within 14 days prior to dosing on C1D1, with the following exceptions: Pregnancy test (within 7 days of dosing; must be negative).

⁵ \pm 2 days. Confirmatory scans should also be obtained 4 weeks following initial documentation of objective response.

⁶ To be done at end of treatment (30 days after last dose of study treatment; may be combined with 30 day safety follow-up, if timing coincides). If subject to initiate new anti-cancer therapy assessments should occur before the first dose of the new therapy.

⁷ Follow-up to occur about every 60 days (\pm 7 days) for first 6 months, every 90 days (\pm 14 days) for 2 years; then every six months (\pm 28 days) for the duration of the study until disease progression or initiation of new anti-cancer therapy.

⁸ After disease progression or initiation of new anti-cancer therapy, contact for survival about every 3 months (± 4 weeks) for the duration of the study after stopping treatment.

⁹ Pathologic review/confirmation of diagnosis by Laboratory of Pathology, NCI (no time limit) and PD-L1 as outlined in Section [5.2.4.1](#). If archival sample is not available, a fresh punch or core biopsy of an appropriate easily accessible tumor deposit will be obtained.

¹⁰ Physical exams to include medical history (i.e., complete at Screening/Baseline; interim on study and in follow-up), vitals, weight, and height (screening only).

¹¹ Chemistry panels include: Acute care, Hepatic, and Mineral.

¹² Diffusing capacity/alveolar volume (DLCO/VA), forced expiratory volume in 1 second (FEV1) for patients with significant pulmonary or smoking history or suspected tumor related pulmonary dysfunction and Transthoracic Echocardiograph for patients with suspected cardiac dysfunction that would increase their risk in receiving protocol treatment.

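### For patients who cannot return after treatment, 3.6 and 3.6.3 request only a local CBC or a symptom call, although Appendix F lists chemistry panels and TSH/T4 at those visits (minor safety point)

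*Combined protocol and SAP*

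**What the plan says.** **Fallback.** For the End of Treatment visit, about 30 days after the last dose, 3.6 provides that if the patient cannot come to the Clinical Center, "a request will be made to have a local physician or laboratory collect a CBC with differential and send the results". If that too is impossible, the patient may be assessed for symptoms by telephone or email. Section 3.6.3 applies the same two steps to follow-up before progression, opening with "If the patient cannot return to the Clinical Center for any of these visits".

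**Calendar.** Appendix F marks chemistry panels and thyroid function at End of Treatment, Safety and Follow-Up (Prior to PD). Footnote 11 states: "Chemistry panels include: Acute care, Hepatic, and Mineral". Section 2.5.2 shows that these panels contain creatinine, ALT, AST and bilirubin. Section 3.6.1 says that testing required at the 30-day safety visit is what the calendar lists, and gives no shorter list for remote patients.

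**Other provisions.**
- 3.6 allows other tests when clinically indicated, and follows patients removed for an unacceptable AE until it resolves or stabilises.
- 3.6.1: "Patients with an ongoing, treatment-related AE of Grade > 1 will be followed until the resolution of the AE", or until it stabilises or new therapy begins.
- 3.6.2 extends safety follow-up to 90 (+14) days because of delayed immune toxicity. The contact may be a call or email, with a "subsequent clinic visit requested in case any concerns are noted".
- 3.9: before removal from study, "effort must be made to have all patients complete a safety visit approximately 30 days following the last dose of study therapy".
- 3.6.4: after confirmed progression or new therapy, "the subject moves into the survival follow-up phase", which needs no clinic visit.

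**The concern.** Tables 12 and 13 grade hepatic irAEs by AST, ALT and bilirubin and renal irAEs by creatinine, and call for high-dose steroids from Grade 3 (hepatic) or Grade 2 (renal). A CBC measures none of these, and a symptom call cannot find a change without symptoms. Thyroid dysfunction likewise cannot be confirmed without TSH and T4. The fallback therefore asks for a blood draw but omits the tests on which the protocol's own management tables act.

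Remote patients are plausible: the trial has a single center, recruits by outside referral and self-referral, and the sponsor thought a fallback necessary. What is at stake is late recognition of a treatable toxicity in an individual patient, under a combination for which 3.1 reports no prior safety experience.

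**Working it through.** The plan gives no figure of its own to reproduce. The check sets the text side by side, then sizes the gap.

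**1. Text, visit by visit**

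| Visit | Appendix F | Requested if the patient cannot return |
|---|---|---|
| 30-day / End of Treatment | CBC, chemistry, TSH/T4 and others; 3.6.1 makes the calendar list the required testing | 3.6: local CBC, else symptom call |
| Follow-up before progression | CBC, chemistry, TSH/T4 and others | 3.6.3: local CBC, else symptom call |
| 90 (+14)-day safety contact | clinic visit or telephone/email | same |

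In the first row 3.6 and 3.6.1 conflict. In the second only the calendar and 3.6.3 differ. No section asks for local chemistry or thyroid tests from a patient who cannot return.

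**2. When scheduled chemistry ends.** Appendix F lists chemistry on days 8 and 22 of cycle 1 and days 1, 8 and 22 of cycles 2-4. Day 22 of cycle 4 is study day 3 x 28 + 22 = 106, the day of the last planned avelumab dose. TSH/T4 is last listed on day 1 of cycle 4, day 3 x 28 + 1 = 85. After a full course the gap thus concerns chemistry changes arising after day 106. The 30-day visit is about day 136. The 90-day contact is about day 196, or day 210 with the +14.

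**3. Rate.** Table 2 (N = 1738) gives 16 hepatitis cases; Table 4 gives nephritis at 0.1%.
- Any grade: 16/1738 = 0.92%; 0.92% + 0.1% = 1.02%. This is an upper bound on patients, since one patient may have both.
- Hepatitis grade 3-5 from Table 2: (11 + 0 + 2)/1738 = 13/1738 = 0.75%. Table 4 reports 0.5%, grade 3 only. Grade 3-5 nephritis is not given.

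**4. Expected patients.** The number of remote patients is not in the documents; 2 to 10 of the ceiling of 25 is an assumption.
- Any grade: 2 x 0.0102 = 0.02 to 10 x 0.0102 = 0.10.
- Grade 3-5 hepatitis: 2 x 0.0075 = 0.015 to 10 x 0.0075 = 0.075.
- If all 25 were remote: 25 x 0.0102 = 0.26 at any grade.

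These counts cover the whole course, including onsets during treatment and onsets with symptoms, so the late, silent number is smaller.

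**5. Thyroid, kept apart.** Thyroid disorders were 98/1738 = 5.64%, giving 2 x 0.0564 = 0.11 to 10 x 0.0564 = 0.56. Pooling them would let one category supply 98 of 114 Table 2 events (86%) and would misstate the hepatic and renal risk.

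**6. How many 3.6.3 draws fall in the safety window.** Visits are every 60 (±7) days. Counted from the last dose, the first is at day 60 and the second no earlier than 120 - 7 = 113, past 90 + 14 = 104. Counted from the 30-day visit, the first is at 30 + 60 = 90. Either way one scheduled 3.6.3 visit lies in the window.

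**The case against.** The strongest reply is that the plan does not set a CBC as the accepted standard. For the 30-day visit, 3.6.1 requires the calendar tests without any trigger and without excepting remote patients; 3.6 permits other tests; and 3.9 asks for effort to complete that visit. All of this stands. A reader might infer that the plan rules out local chemistry, or that every safeguard waits for a symptom or a known AE. The documents support neither. What remains is that the sentence staff would follow for a remote patient names only a CBC, and nothing resolves its conflict with 3.6.1.

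A second reply concerns timing. A reader might take the Table 4 hepatitis median of 3.2 months, set it against the 106 - 8 = 98 days from first to last avelumab dose, and conclude that about half of hepatitis onsets would follow treatment. The documents do not carry that. The Table 4 column is for onset of symptoms, not silent laboratory change; the length of exposure behind it is not given; section 1.3 expects autoimmune events to become apparent mainly in cycle 2 or 3; and chemistry is scheduled throughout those cycles. The upper end of the hepatitis range, 15 months, shows that late onset occurs, but not how often it would here.

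Third, 3.6.3 visits exist to follow disease status, and delayed toxicity has its own section. This is a fair reason to limit the 3.6.3 change to the safety window. It does not remove the gap, because the 3.6.2 contact may itself be a call, and Appendix F already lists chemistry and TSH/T4 at the 3.6.3 visits.

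**Conclusion.** The point holds as a minor patient-safety improvement. The fallback in 3.6 and 3.6.3 leaves out tests that Appendix F lists for the same visits, and for the 30-day visit it also conflicts with 3.6.1. A new silent hepatic or renal abnormality after the last dose could be missed in a patient followed that way.

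The expected number is well under one patient. This rests on single-agent avelumab rates carrying over to the combination, on diagnosed hepatitis and nephritis standing in for silent laboratory rises, and on the assumed count of remote patients. Patients who have progressed are affected only at the 30-day visit, since they then move to survival contact.

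A reader might infer a threat to the trial's endpoints. That is not supported. Response is untouched. For the AE endpoint, 6.1.1 records only serious, related events after 30 days, and 6.1.2.1 counts a laboratory abnormality as an AE only under listed conditions, so any loss is small.

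**What to change.** In 3.6, replace the CBC request with a CBC with differential, chemistry panels (including hepatic panel and creatinine) and TSH/free T4 as listed for the visit in Appendix F, drawn locally. Make the same change in 3.6.3, at least for visits within the 90 (+14)-day window of 3.6.2. Keep the telephone or email check as the last resort. This brings 3.6 into line with 3.6.1 and adds no test that the calendar does not already list.

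The cost is a sentence in each of the two sections and a few more tubes at a draw already being requested. Under 3.8.1 patients may have to pay for outside tests that insurance does not cover, so add a line to 3.8.3 stating whether NIH covers them.
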